# Table 2: Management of QT Prolongation by CTCAE Grade

# 5.7 Treatment of Study Drug-related Infusion Reactions

Nivolumab and the combination therapies may induce infusion or hypersensitivity reactions. If such a reaction were to occur, it may manifest with fever, chills, rigors, headache, rash, pruritus, arthralgia, hypo- or hypertension, bronchospasm, or other symptoms.

Infusion reactions should be graded according to CTCAE vs guidelines. Any Grade 3 or Grade 4 infusion reaction should be reported within 24 h to the PI or designee and reported as an SAE if it meets the criteria.

The nivolumab 30-min infusion will be administered first, with a 30-min rest, followed by the administration of ivosidinib. It may be unclear if an infusion reaction is due to the combination therapy, nivolumab, or to both study drugs. Therefore, one set of treatment recommendations (based on the most conservative treatments for infusion reactions due to either study drug) is

provided below and may be modified based on clinical judgment, local treatment standards and guidelines, and/or specific symptoms, as appropriate:

**For Grade 1 symptoms:** Mild reaction (e.g., localized cutaneous reactions including mild pruritus, flushing, rash), requires infusion rate to be decreased; intervention may be indicated.

Decrease the rate of the study drug infusion until recovery from symptoms.

Remain at bedside and monitor the participant's vital signs until resolution of symptoms. Diphenhydramine 50 mg may be administered at the discretion of the treating physician.

When symptoms resolve, restart the infusion at the original infusion rate.

If a participant has an infusion reaction with nivolumab, combination therapy can be given (without prophylactic medications) if the infusion reaction resolves within 3 h. For scheduling purposes, infusion may be given the next day. Prophylactic pre-infusion medications should be given prior to all subsequent nivolumab infusions.

If a participant has an infusion reaction, prophylactic pre-infusion medications should be given prior to all subsequent infusions.

The following prophylactic pre-infusion medications are recommended prior to future infusions: diphenhydramine 50 mg (or equivalent) and/or paracetamol (acetaminophen) 325 to 1,000 mg at least 30 min before additional study drug administrations.

**For Grade 2 symptoms:** Moderate reaction (i.e., any symptom not listed above [mild symptoms] or below [severe symptoms] such as generalized pruritus, flushing, rash, dyspnea, and hypotension with systolic blood pressure (BP) > 80 mmHg), requires infusion interruption but responds promptly to symptomatic treatment (e.g., antihistamines, nonsteroidal anti-inflammatory drugs, narcotics, corticosteroids, IV fluids); prophylactic pre-infusion medications indicated **for** 24 h.

Interrupt the study drug infusion.

Begin an IV infusion of normal saline, and treat the participant with diphenhydramine 50 mg IV (or equivalent) and/or paracetamol (acetaminophen) 325 to 1,000 mg.

Remain at bedside and monitor the participant's vital signs until resolution of symptoms. Corticosteroid therapy may be administered at the discretion of the treating physician.

When symptoms resolve, restart the infusion at 50% of the original infusion rate; if no further complications ensue after 30 min, the rate may be increased to 100% of the original infusion rate.

Monitor the participant closely. If symptoms recur, immediately discontinue the infusion; no further study drug will be administered at that visit. Administer diphenhydramine 50 mg IV and remain at bedside and monitor the participant until resolution of symptoms.

If a participant has an infusion reaction with nivolumab infusion, combination therapy infusion can be given (without prophylactic medications) if the infusion reaction resolves within 3 h. For scheduling purposes, the combination therapy infusion may be given the next day. Prophylactic pre-infusion medications should be given prior to all subsequent nivolumab infusions.

If a participant has an infusion reaction with a combination therapy, prophylactic pre-infusion medications should be given prior to all subsequent infusions.

The following prophylactic pre-infusion medications are recommended prior to future infusions: diphenhydramine 50 mg (or equivalent} and/or paracetamol (acetaminophen} 325 to 1,000 mg should be administered at least 30 min before additional study drug administrations. If necessary, corticosteroids (up to 25 mg of SoluCortef or equivalent} may be used.

The amount of study drug infused must be recorded.

**For Grade 3 or Grade 4 symptoms:** Severe reaction such as bronchospasm, generalized urticaria, systolic BP< 80 mmHg, or angioedema; Grade 3 symptoms including prolonged symptoms, which require 6 or more hours to respond to symptomatic medication and/or discontinuation of infusion; recurrence of symptoms following initial improvement; hospitalization indicated for other clinical sequelae, such as renal impairment, pulmonary infiltrates; Grade 4: life-threatening; pressor or ventilation support indicated.

Immediately discontinue the study drug infusion. No further study drug will be administered. The amount of study drug infused must be recorded on the case report form (CRF}.

Begin an IV infusion of normal saline, and treat the participant as follows: Recommend bronchodilators, epinephrine 0.2 to 1.0 mg of a 1:1,000 solution for SC administration or 0.1 to 0.25 mg of a 1:10,000 solution injected slowly for IV administration, and/or diphenhydramine 50 mg IV with methylprednisolone 100 mg IV (or equivalent), as needed.

Remain at bedside and monitor the participant's vital signs until recovery from symptoms.

The participant should be monitored until the investigator is comfortable that the symptoms will not recur.

Investigators should follow their institutional guidelines for the treatment of anaphylaxis.

In the case of late-occurring hypersensitivity symptoms (e.g., appearance of a localized or generalized pruritus within 1 week after treatment}, symptomatic treatment may be given (e.g., oral antihistamine, or corticosteroids}.

### 5.8 Nivolumab AEs

Nivolumab treatment should be permanently discontinued for the following:

Any Grade 2 drug-related uveitis, eye pain, or blurred vision that does not respond to topical therapy and does not improve to Grade 1 severity within the OR requires systemic treatment

Any Grade 3 non-skin, drug-related AE lasting> 7 days or recurs, with the following exceptions for laboratory abnormalities, diarrhea, drug-related uveitis, pneumonitis, bronchospasm, hypersensitivity reactions, infusion reactions, and endocrinopathies:

- Grade 3 drug-related diarrhea, uveitis, pneumonitis, bronchospasm, hypersensitivity reaction, or infusion reaction of any duration requires discontinuation.
- Grade 3 drug-related endocrinopathies adequately controlled with only physiologic hormone replacement do not require discontinuation.

- Grade 3 drug-related laboratory abnormalities do not require treatment discontinuation except for the following:
  - Grade 3 drug-related thrombocytopenia > 7 days or associated with bleeding requires discontinuation
  - o Any drug-related liver function test (LFT) abnormality that meets the following criteria require discontinuation:
    - Grade 3 drug-related AST, ALT, or total bilirubin requires discontinuation
    - Concurrent AST or ALT> 3x ULN and total bilirubin > 2x ULN

Any drug-related Grade 4 endocrinopathy and Grade 3 adrenal insufficiency requires discontinuation.

Any Grade 4 drug-related AE or laboratory abnormality (including but not limited to creatinine, AST, ALT, or total bilirubin), except for the following events, which do not require discontinuation:

- Grade 4 neutropenia ::; 7 days
- Grade 4 lymphopenia or leukopenia
- Isolated Grade 4 amylase or lipase abnormalities that are not associated with symptoms or clinical manifestations of pancreatitis
- Isolated Grade 4 electrolyte imbalances/abnormalities that are not associated with clinical sequelae and are corrected with supplementation/appropriate management within 72 h of their onset

Any drug-related Grade 4 endocrinopathy and Grade 3 adrenal insufficiency requires discontinuation.

Any event that leads to delay in dosing lasting> 8 weeks from the previous dose requires discontinuation, with the following exceptions:

- Dosing delays to allow for prolonged steroid tapers to manage drug-related AEs are allowed.
- Dosing delays lasting > 8 weeks from the previous dose that occur for non-drug-related reasons may be allowed if approved by the Lead Investigator.

Prior to re-initiating treatment in a participant with a dosing delay lasting> 6 weeks, the Lead Investigator must be consulted. Tumor assessments should continue as per protocol even if dosing is delayed. Periodic study visits to assess safety and laboratory studies should also continue every 6 weeks or more frequently if clinically indicated during such dosing delays.

Any AE, laboratory abnormality, or intercurrent illness, which presents a substantial clinical risk to the participant with continued nivolumab dosing as assessed by the treating investigator.

# 5.9 Management of Nivolumab AEs

Participants should receive appropriate supportive care measures as deemed necessary by the treating investigator. Where appropriate, these guidelines include the use of oral or IV treatment with corticosteroids as well as additional anti-inflammatory agents if symptoms do not improve with administration of corticosteroids. Note that several courses of steroid tapering may be necessary as symptoms may worsen when the steroid dose is decreased. For each disorder, attempts should be made to rule out other causes such as metastatic disease or bacterial or viral infection, which might require additional supportive care. The treatment guidelines are intended to be applied when the investigator determines the events to be related to nivolumab.

It may be necessary to perform conditional procedures such as bronchoscopy, endoscopy, or skin photography as part of evaluation of the event.

- Pneumonitis:
  - For Grade 2 events, treat with systemic corticosteroids. When symptoms improve to Grade 1 or less, steroid taper should be started and continued over no less than 4 weeks.
  - o For **Grade 3-4 events**, immediately treat with IV steroids. Administer additional antiinflammatory measures, as needed.
  - o Add prophylactic antibiotics for opportunistic infections in the case of prolonged steroid administration.
- Diarrhea/Colitis:

Participants should be carefully monitored for signs and symptoms of enterocolitis (such as diarrhea, abdominal pain, blood or mucus in stool, with or without fever) and of bowel perforation (such as peritoneal signs and ileus).

- All participants who experience diarrhea/colitis should be advised to drink liberal quantities of clear fluids. If sufficient oral fluid intake is not feasible, fluid and electrolytes should be substituted via IV infusion. For Grade 2 or higher diarrhea, consider GI consultation and endoscopy to confirm or rule out colitis.
- o For **Grade 2 diarrhea/colitis** that persists greater than 3 days, administer oral corticosteroids.
- For **Grade 3 or 4 diarrhea/colitis** that persists> 1 week, treat with IV steroids followed by high dose oral steroids.
- o When symptoms improve to Grade 1 or less, steroid taper should be started and continued over no less than 4 weeks.
- o Type 1 diabetes mellitus (if new onset, including diabetic ketoacidosis [DKA]) or Grade 3 Hyperglycemia, if associated with ketosis (ketonuria) or metabolic acidosis (DKA)
  - For TIDM or Grade 3-4 hyperglycemia

Insulin replacement therapy is recommended for Type I diabetes mellitus and for Grade 3-4 hyperglycemia associated with metabolic acidosis or ketonuria.

Evaluate participants with serum glucose and a metabolic panel, urine ketones, glycosylated hemoglobin, and C-peptide.

- Hypophysitis:
  - For Grade 2 events, treat with corticosteroids. When symptoms improve to Grade 1 or less, steroid taper should be started and continued over no less than 4 weeks.
     Replacement of appropriate hormones may be required as the steroid dose is tapered.
  - For Grade 3-4 events, treat with an initial dose of IV corticosteroids followed by oral corticosteroids. When symptoms improve to Grade 1 or less, steroid taper should be started and continued over no less than 4 weeks. Replacement of appropriate hormones may be required as the steroid dose is tapered.
- Hyperthyroidism or Hypothyroidism:

Thyroid disorders can occur at any time during treatment. Monitor participants for changes in thyroid function (at the start of treatment, periodically during treatment, and as indicated based on clinical evaluation) and for clinical signs and symptoms of thyroid disorders.

- o Grade 2 hyperthyroidism events (and Grade 2-4 hypothyroidism):
  - In hyperthyroidism, non-selective beta-blockers (e.g. propranolol) are suggested as initial therapy.
  - In hypothyroidism, thyroid hormone replacement therapy, with levothyroxine or liothyronine, is indicated per standard of care.
- o Grade 3-4 hyperthyroidism
  - Treat with an initial dose of IV corticosteroid followed by oral corticosteroids.
     When symptoms improve to Grade 1 or less, steroid taper should be started and continued over no less than 4 weeks. Replacement of appropriate hormones may be required as the steroid dose is tapered.
- Hepatic:
  - o For **Grade 2** events, monitor liver function tests more frequently until returned to baseline values (consider weekly).
    - Treat with IV or oral corticosteroids
  - o For Grade 3-4 events, treat with IV corticosteroids for 24 to 48 h.
  - o When symptoms improve to Grade 1 or less, a steroid taper should be started and continued over no less than 4 weeks.
- Renal Failure or Nephritis:
  - o For Grade 2 events, treat with corticosteroids.
  - o For Grade 3-4 events, treat with systemic corticosteroids.

• When symptoms improve to Grade 1 or less, steroid taper should be started and continued over no less than 4 weeks.

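### Section 5.9 lets Grade 3-4 diarrhea/colitis persist more than 1 week before its written steroid trigger, 4 days later than the Grade 2 trigger, with no reason given

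*Combined protocol and SAP*

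**What the plan says.** Section 5.9 applies to events that the investigator judges related to nivolumab. Its diarrhea/colitis entry has two steroid bullets.

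- Grade 2: for an event "that persists greater than 3 days, administer oral corticosteroids".
- Grade 3 or 4: for an event "that persists> 1 week, treat with IV steroids followed by high dose oral steroids".

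The same entry adds other safeguards: monitoring for enterocolitis and perforation, fluids by vein when drinking is not feasible, and "For Grade 2 or higher diarrhea, consider GI consultation and endoscopy to confirm or rule out colitis". The section opens with a general statement of discretion: "Participants should receive appropriate supportive care measures as deemed necessary by the treating investigator". It also asks that other causes, including infection, be ruled out.

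Section 5.8 requires permanent discontinuation of nivolumab for Grade 3 drug-related diarrhea regardless of how long it lasts. Grade 4 drug-related events generally require it too. Section 5.8 says nothing about when to start steroids.

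**The concern.** Treatment intensity rises with severity, from oral to IV steroids, but the written starting point moves the other way. A site that follows the bullets literally would begin steroids later for an event that starts at Grade 3-4 than for one that stays at Grade 2. Section 5.5.1.1 refers nivolumab safety issues to 5.9, and nothing elsewhere in the protocol gives an earlier steroid start for Grade 3-4 diarrhea/colitis. The bullet is therefore the only timing a site will find. What is at stake is prompt treatment of a severe immune-related toxicity, not the trial's inference.

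**Working it through.** No sample size, error rate or event count enters here. The check is a comparison of text and one subtraction.

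**Step 1: the two triggers.** Both come from the diarrhea/colitis entry of 5.9.

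- Grade 2: more than 3 days, oral corticosteroids.
- Grade 3-4: more than 1 week = more than 7 days, IV steroids and then high-dose oral.
- Difference: 7 - 3 = 4 days later at the higher grades.

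**Step 2: the other steroid instructions in 5.9.** The table records what the text states about a wait. Silence is recorded as silence, not as zero.

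| Condition | Grade 2 | Grade 3-4 |
|---|---|---|
| Pneumonitis | no timing ("For Grade 2 events, treat with systemic corticosteroids") | no wait ("immediately treat with IV steroids") |
| Diarrhea/colitis | more than 3 days | more than 1 week |
| Hypophysitis | no timing ("For Grade 2 events, treat with corticosteroids") | no timing ("For Grade 3-4 events, treat with an initial dose of IV corticosteroids followed by oral corticosteroids") |
| Hyperthyroidism | no steroid instruction | no timing |
| Hepatic | no timing | no timing (the 24 to 48 h is a length of treatment) |
| Renal | no timing | no timing |

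Of the six Grade 3-4 steroid instructions, only diarrhea/colitis states a wait. One of the other five says to treat at once; four give no timing. Diarrhea/colitis is also the only condition with a stated wait at Grade 2. Some wait may thus be deliberate for this condition, for instance while infection is excluded. That could explain a wait at Grade 2, but not a longer one when the event is worse.

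**Step 3: who is exposed to the difference.**

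- A participant at Grade 2 for more than 3 days before worsening has already met the oral-steroid trigger.
- A participant whose event begins at Grade 3-4, or reaches it within those 3 days, has not. The Grade 2 bullet is worded for Grade 2 only, so the more-than-1-week trigger is the only one left.

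**Step 4: how many.** The documents give no rate of Grade 3-4 diarrhea/colitis for the combination. Section 1.5 reports diarrhea in 26.2% of 168 participants on ivosidenib, but that is neither restricted to severe grades nor to nivolumab-related events. I make no estimate of the number affected.

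**The case against.** **Discretion.** Section 5.9 leaves supportive care to the treating investigator, says steroids are used where appropriate, and never says to withhold them. Section 5.13.4 leaves treatment of intercurrent conditions to the investigator under local standards, and Section 7.5 promises appropriate care and close monitoring after a DLT. Under 5.8 the suspected drug is stopped without any wait. All of this stands and makes an actual delay less likely. It does not correct the bullet, which still gives the only number for the severe grades.

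**Different treatments.** One trigger is for oral steroids, the other for IV followed by high-dose oral. The two could be read as a ladder: oral after 3 days, then IV if severe disease lasts a week. The point that route and intensity differ stands, and the 4 days should be described with that in mind. But the text does not state a ladder, and an event that starts at Grade 3 has no oral rung to stand on.

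**Stronger readings that a reader might infer.**

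- *That participants with severe colitis will wait a week for steroids.* The documents do not support this. The 4 days is a difference between guideline triggers, not a required delay.
- *That every other Grade 3-4 event in 5.9 must be treated immediately.* Only pneumonitis says so; the others are silent on timing.
- *That 5.8 and 5.9 contradict each other.* They govern different actions, stopping nivolumab and starting steroids, so no interval between them can be calculated.
- *That 7.5 sets a 3-day standard of urgency.* It is a rule for counting DLTs, and without anti-diarrheals it counts Grade 3-4 diarrhea only after more than 3 days, which itself tolerates a wait. It is weak evidence on steroid timing.

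**Conclusion.** The concern holds in a limited form. For diarrhea/colitis that begins at or quickly reaches Grade 3-4, the only written steroid trigger is 4 days later than the trigger for Grade 2, and the protocol gives no reason. This is an inconsistency in safety guidance that should be fixed because it concerns severe toxicity. It is not a statistical flaw: no endpoint, DLT count or pause boundary changes.

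The conclusion rests on reading each bullet as applying only to the grades it names, and on no earlier timing being supplied elsewhere in the protocol. The nivolumab Investigator Brochure is not among the documents, so whether it gives different timing is unknown.

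**What to change.** Remove the whole persistence condition from the Grade 3-4 diarrhea/colitis bullet, so that it calls for prompt IV steroids, then high-dose oral steroids, for any nivolumab-related Grade 3 or 4 event. Deleting only the reference to one week is not enough: it would leave an event that merely persists as the trigger, with no time attached. If the authors want to keep a wait, they should state an explicit limit no later than the Grade 2 trigger of 3 days. If there is a reason for a longer wait at Grade 3-4, the protocol should give it. The investigator and the nivolumab supplier should confirm the wording. Sections 5.8 and 7.5 need no change.

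The cost is an amendment to one bullet, with no added procedures, visits or participants. The small downside is that some participants may receive steroids before an infectious cause is fully excluded. The existing instruction in 5.9 to rule out other causes stays in place.

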### 5.10 Duration of Subject Participation

### 5.10.1 Treatment Duration

Treatment with ivosidenib and nivolumab will continue until any of the conditions for withdrawal of study treatments are met - as detailed in 4.4.1.

Following discontinuation of study treatment, participants are to attend a Follow-up Visit at least 28 days and no more than 33 days after the last dose for study assessments. When study treatment is withheld from a participant to resolve toxicity and the participant does not subsequently restart treatment, EOT is defined as the date when the study drug was first held. Participants should proceed with EOT assessments, safety and PFS follow-up. If the decision to not restart study treatment occurs outside of the 28-day safety follow-up window, the participant should proceed with PFS follow-up.

### 5.11 Treatment Compliance

Participants will be dispensed the appropriate number of labeled bottle(s) of ivosidenib for at least 28 days of dosing on Day 1 of each cycle. The ivosidenib should be taken at approximately the same time each day. On clinic days, the ivosidenib should be taken any time prior to the nivolumab infusion. The participant will be asked to return all bottles and unused tablets (or empty bottles) on Day 1 of each cycle or at their next study visit for assessment of compliance with the dosing regimen.

Participants will be given a dosing diary for each treatment cycle. They should record relevant information regarding their study treatment in the diary (e.g., confirmation that each daily dose was taken, reasons for missed doses). Treatment compliance will be assessed based on return of unused drug and the dosing diary.

### 5.12 Study Treatment Accountability

Accountability for the study treatment at the study site is the responsibility of the Investigator. The Investigator will ensure that the study treatment is used only in accordance with this protocol. Where allowed, the Investigator may choose to assign drug accountability responsibilities to a pharmacist or other appropriate individual.

The Investigator or delegate will maintain accurate drug accountability records indicating the drug's delivery date to the site, inventory at the site, use by each participant, and disposal of the drug. These records will adequately document that the participants were provided the doses as specified in the protocol and should reconcile all study treatment Accountability records will include dates, quantities, batch/serial numbers, expiration dates (if applicable), and participant numbers.

Study treatment must not be used for any purpose other than the present study. Study treatment that has been dispensed to a participant and returned unused must not be re-dispensed to a different participant.

Participants will receive instructions for home administration of study treatment along with a diary to record the date and time of each dose, as well as the number of tablets taken.

All unused and used study treatment should be retained at the site until they are inventoried and verified by study site personnel and/or the study monitor. All used, unused, or expired study treatment

will be returned to the Drug Manufacturer or its designee or if authorized, disposed of at the study site per the site's Standard Operating Procedures (SOPs) and documented. All material containing ivosidenib will be treated and disposed of as hazardous waste in accordance with governing regulations.

